Subjects may advise the CRC or investigators of their desire to withdraw from this research at any time, prior to their second (final) study visit. Following the second visit, their data will be deidentified, and will not be able to be removed. The investigators may remove subjects who do not complete the second visit (i.e. missing data), do not present for their scheduled well-child visit, or are lost to follow up.

9) Risks to subjects*

As reading with children is considered to be helpful for their development, this study involves minimal to no risk to subjects. However, the following risks/inconveniences are possible:

- *Financial risks* may involve the use of cell phone data minutes, though these are expected to be small.
- The well-child visit (checkup) may take longer than usual, due to *time* spent completing surveys. We will try to finish these during normal waiting time before the doctor is ready to see participating families, so that inconvenience is minimal, and the visit goes smoothly. We will be working with clinic staff to help make sure this happens.
- Increased screen-based media use is possible via encouraging use of a smartphone-based application (RS app), and this possibility is explored via one of our study aims. By contrast, families in the control group will receive a specially designed children's book discussing alternatives to screen time.

10) Potential benefits to subjects*

Potential benefits to subjects include:

- Increased knowledge of healthy reading practices to try at home (very likely).
- Increased knowledge about the child's emotional and language development (likely).
- Improved emotional and language *development* through more healthy reading practices to try at home (possible, the purpose of the study). The mechanism of reading instruction (RS app) is unproven at this time.

11) Provisions to protect the privacy interests of subjects

Subjects will be approached as discretely as possible via a trained CRC in the clinic waiting area, and invited to discuss the study in an area that is as quiet and private as possible. For those expressing interest, written informed consent will be obtained in either a private area of the waiting room or in a private exam room, and all data will be collected in a private exam room. As this study involves minimal risk, initial discussion of the aims of the study or eligibility requirements in the waiting area does not represent a major risk to subject privacy, though the CRC will be advised to be as discreet as possible.

12) Provisions to maintain the confidentiality of data

Screening and survey data will be directly entered by the CRC into REDCap (www.REDCap.org), a secure, HIPAA-capable web-based data management tool, to the greatest degree possible (demographics and select parental surveys). All paper-based data will be transcribed into REDCap as expeditiously as possible. All subjects will be assigned a unique Study ID in REDCap, and at the conclusion of data collection for all subjects, all identifying information such as names and phone numbers will be deleted. Biostatisticians at Children Inc. and the principal investigator will only download deidentified data via REDCap for analysis, and then store this data on password-protected servers at their respective institutions (Children Inc. and CCHMC). REDCap data will be stored on secure, password-protected servers hosted by Cincinnati Children's Division of Biomedical Informatics, with state of the art security features. Hard copy records will be restricted to IRB-approved study personnel in locked cabinets at CHC@CCMC. Hardcopy data will be destroyed within 3 years of conclusion of the study.

13) Medical care and compensation for injury

This study involves minimal risk, and such provisions are not required.

14) Cost to subjects

There are no costs involved with participation in this research, other than use of smartphone data minutes using the RS application (if applicable; would not result in any cost in the case of increasingly common unlimited data plans), expected to be minimal. The RS application is completely free, with no special accounts needed.

15) Consent process

- Written informed consent will be administered via a trained CRC in a private section of the waiting area or private exam room at CHC@CCMC.
- A single CRC to be hired via the Weitzman Institute will be solely responsible for informed consent.
- Informed consent will cover all aspects of the study included on the consent form, in plain English, anticipated to take less than 5 minutes. The ability to comprehend the informed consent documents in plain English without a translator is a requirement for inclusion in this study.

- Non-English speaking families are excluded from this pilot study due to restrictions on time, budget, and the need to minimize covariates such as language spoken at home in our analyses, especially as bilingual children are known to have short-term language delays likely to influence our findings. The RS app is also not currently available in Spanish. In the future, we plan to expand our research to non-English speaking households.
- As this study involves convenience sampling in the waiting area, there is no lag expected between approach for consent, administration of consent, and enrollment in the study for those interested.
- The CRC administering informed consent will emphasize that participation in this study is optional and voluntary, and that their child will receive the same well-child care regardless of participation, including via the Reach Out and Read program.
- Consent from one custodial parent is all that will be required for this research. “Custodial” parent will be defined as with necessary permission to accompany the child to the doctor at the current visit, and who lives with the child at home and would have the opportunity to consistently read to them. As reading with children is generally considered to be beneficial, we feel that permission from one parent is adequate for our study design. If, by small chance, the second parent or custodial caregiver protests this enrollment and requests removal, the child will be removed from the study.
- If the child is accompanied by another family member such as an aunt or grandparent, they will not be enrolled in this study, unless this family member has full-time legal custody of the child, authorized by a court order.
- This study clearly involves children (age 6-12 months and 18-24 months old), by any definition. Children of this age can not reasonably be expected to provide consent or assent, and will not be asked to do so.

16) Process to document consent in writing

Written informed consent will be documented on the IRB-approved consent form accompanying this application, written in plain English per specifications and summarized in person via the CRC. One copy of this form will be given to the consenting family member, and the other securely stored in a locked cabinet dedicated to this study at CCMC.

17) Vulnerable populations

This research involves young children under the care of their parent(s) or custodial caregiver, who will be delegated responsibility to make an informed consent on their behalf. As this study involves minimal risk, and shared reading is generally considered beneficial, the child’s vulnerability to harm is negligible.

18) Drugs or Devices

This study does not involve drugs or devices.

19) Multi-site Human Research*

All data collection and intervention for this study will take place at a single site at CHC@CCMC. Data will be securely stored in a REDCap database hosted at Cincinnati Children's Division of Biomedical Informatics, accessed via the CRC using a unique password, and other access restricted to IRB-approved study personnel. All data downloaded for analysis by biostatisticians at Children Inc. or the principal investigator will be in deidentified form, and then stored in password-protected servers at the respective institutions (Children Inc. and CCHMC).

20) Sharing of results with subjects

Results from this study will not be directly shared with subjects. For children identified as being at risk for language delay via LENA Snapshot scores at their second study visit (standard scores <77), their primary pediatric provider will be notified by [name] from CHC@CCMC, to discuss with families as soon as possible.

21) In the Event of Distress

In the unlikely event that a participant in this study becomes distressed, such as vomiting, the CRC will notify clinic staff at CHC@CCMC immediately to address the issues. No further evaluation or testing will be attempted unless specifically requested by the family and poses no discomfort to the child. [name] will be notified via the most efficient means possible to advise of such an event, to follow up with the family and clinical providers as appropriate.

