Overview/Rationale: Our strategy is to conduct an innovative experiment that is achievable within 15 months, providing data for a larger, longer-term longitudinal study exploring the impact of “enhanced” ROR on home reading environment and cognitive and social-emotional development. This study involves a low-SES population of infants and toddlers at-risk for adverse cognitive and social-emotional outcomes, during a foundational period of early brain development, who stand to benefit from effective early intervention to improve the quality of cognitive stimulation and nurturing in the home. Such innovation is needed, given challenges to providing consistent, effective dialogic reading training in busy clinical settings, where such at-risk families are uniquely accessible. The resources and infrastructure are in place via ROR for this work to commence expeditiously with high probability of success.

Preliminary data: A pilot process evaluation field test of 26 predominantly African-American and Urban Appalachian low-income families enrolled in ROR, demonstrated an overwhelmingly positive response to the RS app with 100% of participants rating the video as motivational and 95% rating the reminders as helpful. Quotes from participants included:

“The video talked about singing and when I did that she seemed to really like it and become engaged.”

“My grandson loves it. He’s really interested and we are happy to get the reminders.”

“We all know that it’s important to read to your child, but we don’t always remember every day....having the reminders helped me to actually do the reading more.”

A separate pilot study involving ROR families found that those who already knew about the importance of reading aloud considered videos incorporated into the RS app to be valuable in explaining how to read more interactively with their young children. By contrast, a recent MRI-based study involving video observations of 22 low-SES mothers

reading with their preschool-age children found low verbal interactivity and engagement despite prior access to home visiting and ROR, suggesting a need for improved dialogic training.²⁰

Other recent work that will support this proposed project includes initial validation of brief measures assessing shared/dialogic reading quality (DialogPR) and screen-based media use in the home (ScreenQ).⁴⁶

6) Setting of the Human Research

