The principal investigator ([name]) is a primary care pediatrician who has conducted innovative, reading-related research involving young children with a high degree of success, including randomized trials of home reading environment⁴⁵, development of clinic-based screening tools,⁴⁶ video observations of parent-child reading quality,^{19, 20} and the application of functional MRI to explore the effects of home reading environment,

including shared reading quality, on the developing brain.^{19, 20, 37} Addressing younger infants and toddlers in this study during critical stages of early brain development is a natural extension of this work, and would build on a cohesive eco-bio-developmental model⁴⁷ of the influence of home reading environment on emergent literacy. Prior to the launch of this study, the principal investigator will travel to the CHC@CCMC host site to discuss and train the study team in this protocol, specifically the research coordinator, including practice “role play” sessions.

A full-time clinical research coordinator (CRC) will be recruited for this study in cooperation with the Weitzman Institute, a community-based research center affiliated with CHC@CCMC dedicated to quality improvement and research in primary care for the underserved. The CRC will be trained in this study protocol via the principal investigator ([name]), the on-site medical director and co-principal investigator ([name]), and a co-investigator from the national ROR program ([name]). The CRC will then recruit the 248 children in our desired age ranges (124/category) via convenience sampling during regularly scheduled well-child visits. Full enrollment within 6 months is feasible given historical well-visit volumes for these ages (40/month meeting enrollment criteria) at the participating clinic at CHC@CCMC. The CRC will optimize enrollment efficiency factoring scheduled well-visit volumes and demographic needs (age), via advance communication with clinic managers. Biostatisticians affiliated with Children, Inc., will perform all required statistical analyses, accessing data via a secure REDCap database housed at CCHMC Division of Biomedical Informatics. Application developers aligned with Children, Inc., will be available to perform any required technical modification or “troubleshooting” of the RS application.

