Study Design: This is a prospective, randomized controlled trial involving 2 age categories of low-SES caregiver-child dyads served by the ROR program, each followed for 6 months. For each category, a baseline assessment (pre-) and an outcomes assessment (post-) will be conducted, to explore effects of “enhanced” ROR using the RS app. Category 1 will involve 6 month-old infants, followed until they are 12 months old. Category 2 will involve 18 month-old toddlers, followed until they are 24 months old. Recruitment, informed consent, behavioral testing and intervention will take place at a high-volume primary care clinic based in a major, urban academic medical center in Connecticut (Community Health Center, Inc. at Connecticut Children’s Medical Center; CHC@CCMC). Providers in the clinical sites are trained in child development and the administration of ROR during well-child visits between birth and age 5, including those involved with our study at 6, 12, 18, and 24 months old.

A graphic of our study design is provided in **Figure 1** below. Families assigned to the control arm in each age category will receive customary ROR, including the provision of an age-appropriate children’s book, and reading-related developmental surveillance and anticipatory guidance. In addition, control families will receive a new children’s book reinforcing AAP screen-based media recommendations.⁴⁸ Families in the intervention arm in both age categories will receive “enhanced” ROR involving the provision of the **Rx for Success** (RS) application at the baseline visit (6 months old and 18 months old, respectively). No additional intervention will take place, other than text messages and other content built into the RS application.

a) Recruitment Methods

Sample Size/Power Analysis: Via our CRC, we will recruit 248 children in 2 age categories: approximately 6 months old (infants, n=124), and approximately 18 months old (toddlers, n=124) via convenience sampling in the CHC@CCMC clinic waiting room

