during regularly scheduled well-child visits. This study will be powered based on the primary language outcome measure (LENA Snapshot). For a two-group (intervention/control), pre-post repeated-measure analysis with two age categories (6-12 months, 18-24 months), an ANCOVA model will be applied for both age categories and their interaction, to assess the difference in language scores between intervention and control groups. For this study, at least 180 subjects will be needed to have 80% statistical power to detect slightly greater than medium effect size (Cohen $f=0.30$), controlling for the baseline pre-measurement with a two-sided significance level of 0.05. This effect size was determined considering the 2008 National Early Literacy Panel Report, which examined 16 studies and reported an effect size of 0.6 for dialogic reading on language outcomes ($d=0.6$; Shanahan, et al).⁴⁹ A separate meta-analysis of 18 studies that tested dialogic reading intervention found average effect size for language outcomes and vocabulary of 0.29 and 1.02, respectively.⁸ However, these reports largely involved preschool- and school-age children, and no studies to our knowledge have reported effect sizes of dialogic reading for language in infants and toddlers.

We anticipate that full enrollment for this study within 6 months is feasible given historical well-visit volumes for these ages (40/month meeting enrollment criteria) at the participating clinic at CHC@CCMC. The CRC will optimize enrollment efficiency factoring scheduled well-visit volumes and demographic needs (age), via weekly communication regarding clinic schedules with clinic managers. The CRC will identify the arrival and registration of potential participants by monitoring the daily schedule (in Centricity) to identify well child visits for children of the appropriate age groups, and will greet them in the waiting room. For enrolled patients only, the CRC will also monitor scheduled encounters (in e-Clinical Works) to identify upcoming appointments for the follow-up (post-intervention) visit, and will monitor arrival in Centricity. The CRC will approach families in the waiting area, confirm that the child meets inclusion criteria by age, and present the major aims of the study in plain language:

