“We are conducting a research study looking at how different ways of providing tips about reading with young children affects attitudes towards reading and early child development. This will involve a little extra time at today’s checkup to ask some questions, and at another checkup in 6 months. You will be compensated for your time. Would you be interested in learning more?”

For those expressing interest, written informed consent will then be administered via the CRC in a quiet area of the clinic waiting room, or private room if available, during the same visit where baseline data collection and intervention will take place. The CRC will review the form in plain language, including details about inclusion/exclusion, aims, incentives, and that participation is voluntary.

Participants will receive a gift card valued at approximately \$25 as compensation for time and travel, with \$10 provided at enrollment (pre-) and \$15 provided at follow-up testing (post-), each taking place during normally scheduled well-child visits. All children will receive a new children’s book per standard ROR practice. Participants in the control arm will receive an additional, new, age-appropriate children’s book reinforcing screen-based media reduction (*Baby Unplugged: Play*), retail value \$7.99.

Study Advertisement: To optimize enrollment and reduce the burden of surprise for families being approached in the waiting room, a brief postcard developed by Reach Out

and Read will be distributed to eligible families at well-child visits immediately preceding those for of our study (i.e. at 4 month visit and 15 month visit, respectively). This will advise them that at their next visit, they may be eligible to participate in this study, describe the study in very general terms, and also note the financial incentive.

Inclusion and Exclusion Criteria: Accounting for a potential 10% attrition rate, at least 200 subjects with 100 in each age category is recommended for this study. We anticipate that 248 should be ample, given variation in effect sizes reported, uncertainty for those in younger children, and higher than usual attrition for this high-risk population.

Inclusion criteria for this study are:

- Gestation of at least 34 weeks,
- Age at initial screening 6 months (5.75 months-7.5 months) or 18 months old (17-21 months).
- No documented history of major neurological insult such as intracranial hemorrhage or V-P shunt.

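### Does an accrual of 40 eligible children a month contradict the claim that 248 can be enrolled in 6 months?

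*Protocol*

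**What the plan says.** Section 7 of the protocol (Resources available to conduct the Human Research) gives the target: "The CRC will then recruit the 248 children in our desired age ranges (124/category". The next sentence gives the feasibility claim: "Full enrollment within 6 months is feasible given historical well-visit volumes for these ages (40/month meeting enrollment criteria". Section 8a (Recruitment Methods) repeats it almost word for word: "within 6 months is feasible given historical well-visit volumes for these ages (40/month meeting enrollment criteria". Neither place says whether the 40 covers both ages together or each age separately, and no consent or refusal rate appears anywhere.

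Four other statements bear on the point:

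- **Numbers needed.** Section 8a requires at least 180 children for 80% power. After a 10% allowance for attrition, the paragraph on inclusion and exclusion criteria says "at least 200 subjects with 100 in each age category is recommended for this study". It explains 248 as a further margin for uncertain effect sizes and higher attrition.
- **Follow-up.** Section 8 describes the two age groups as "each followed for 6 months".
- **Overall duration.** The overview in section 5 calls the project "achievable within 15 months".
- **Consent.** Section 15 says "A single CRC to be hired via the Weitzman Institute will be solely responsible for informed consent" and also "If the child is accompanied by another family member such as an aunt or grandparent, they will not be enrolled in this study", with an exception for a relative who has full-time legal custody under a court order.

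**The concern.** The 40 are described as already meeting the enrolment criteria. If they are the total for both ages, six months' supply is a ceiling, and that ceiling lies below the target. The stated period would then fail on the protocol's own figures even with no refusals.

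Refusals are to be expected. Families are approached in a waiting room, participation is voluntary, and one coordinator handles every consent. The margin between 180 and 248 is explained by attrition and effect-size uncertainty, not by families who decline.

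At stake is whether the enrolment period, and the 15-month duration that depends on it, can be believed. If enrolment were cut off at month 6 with low uptake, the number needed for power might also be missed.

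**Working it through.** **Inputs from the protocol.** Target 248, or 124 per age category (section 7). Volume 40 eligible per month and enrolment period 6 months (sections 7 and 8a). Number for power 180 (section 8a), and 200 after 10% attrition (inclusion and exclusion criteria). Follow-up 6 months (section 8). Duration 15 months (section 5). The protocol gives no consent rate, so every rate below 100% is an assumption.

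**The protocol's own figures.** The attrition step reproduces: 180/(1 − 0.10) = 200. The enrolment claim does not reproduce if 40 is the total:

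- Supply in six months: 40 × 6 = 240, or 120 per category on an even split, against 124.
- Shortfall: 248 − 240 = 8, and 8/248 = 3.2%.
- Rate needed: 248/6 = 41.3 per month.
- Time needed at 40 per month: 248/40 = 6.2 months.

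**If 40 is per age category.** Supply is 2 × 40 × 6 = 480. Uptake needed is 248/480 = 51.7%, and the six-month claim holds.

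**Does the gap matter at full uptake, taking 40 as the total?** 240 exceeds 200. After 10% attrition, 240 × 0.90 = 216, which exceeds 180. Enrolment plus follow-up takes 6.2 + 6 = 12.2 months, inside 15.

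**Effect of refusals, taking 40 as the total (assumed consent rates).**

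| Consent | Enrolled in 6 months | Months to 200 | Months to 248 | Months to 248, plus 6 |
|---|---|---|---|---|
| 100% | 240 | 5.0 | 6.2 | 12.2 |
| 90% | 216 | 5.6 | 6.9 | 12.9 |
| 80% | 192 | 6.25 | 7.75 | 13.75 |
| 70% | 168 | 7.1 | 8.9 | 14.9 |
| 60% | 144 | 8.3 | 10.3 | 16.3 |

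Six months reaches 200 at a consent rate of 200/240 = 83% or more. Allowing 6 months for follow-up leaves 15 − 6 = 9 months for enrolment, with 9 × 40 = 360 eligible. Then 248 fits if consent is at least 248/360 = 69%, and 200 fits if it is at least 200/360 = 56%. These thresholds leave no time for start-up or analysis; the protocol does not say whether the 15 months includes them.

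**The case for a change.** The strongest case for a change runs as follows. The wording refers to the two ages together, so the combined total is the more natural reading, and on that reading the claim needs more than 100% uptake. The other reading needs about 52%. A reader who cannot tell these apart cannot judge feasibility at all. With realistic refusal, six months could fall below 200 (consent under 83%), or even below 180 before any attrition (consent under 180/240 = 75%). The custody rule in section 15, the exclusion of siblings who present later, and the reliance on one coordinator could each reduce the yield further. Enrolment rate and period are protocol content, so this cannot be left to a statistical analysis plan.

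Part of this stands. The unit of the 40 is missing, the consent rate is unstated, and on the combined reading the six-month figure is optimistic.

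The rest does not carry far:

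- **Reading.** The sentence just before the claim in section 7 counts children by age category, so a per-category 40 is not strained. It is also the reading on which the claim works.
- **Refusal.** The low yields at month 6 matter only if enrolment stops then, and no rule says so. The protocol also takes steps to encourage uptake: a postcard at the preceding visit, a gift card, and planning around clinic schedules.
- **Coordinator.** The post is full-time, and 40 a month is about 2 per working day, assuming 20 working days. Nothing shows that families would be lost for this reason.
- **Custody and siblings.** Whether such children are already left out of the 40 cannot be told from the text.

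**Conclusion.** The arithmetic is correct but conditional. If 40 a month is the total for both ages, the protocol's figures fall short of 248 by 8 children, or 0.2 months, at full uptake. If it is per category, there is no shortfall. A discrepancy that a permitted reading removes, and that is otherwise about 3% of a round historical volume, is a loose feasibility remark and not an error in the plan.

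The heavier consequences all come from consent rates that the reader must supply. Even then, on the combined reading, the overall duration holds for 248 children down to about 69% consent, and for the recommended 200 down to about 56%. Both thresholds assume 6 months of follow-up and no time set aside for start-up or analysis.

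The accrual figure does not enter the power calculation, and the target is a number of children, not a closing date. Writing down the unit and an assumed consent rate would make the text clearer, but sample size, design, analysis and the interpretation of the results would all stay the same. No change to the plan follows.
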